9.3.3.2 Incidence tables

The following tabulations were produced overall and for each age group, in total and by treatment group (placebo/dose level/overall active) on the SS for the randomized blinded treatment period.

- TEAEs overall and by system organ class and preferred term
- TEAEs by maximum severity, overall and by system organ class and preferred term
- Severity of TEAEs, overall and by system organ class and preferred term
- Severe TEAEs, overall and by system organ class and preferred term
- Severe TEAEs considered related to IP, overall and by system organ class and preferred term

³ Application site disorders are AEs with 'Application and instillation site reactions' in their MedDRA-coded HLTs.

⁴ Local AESI are identified as detailed in [Section 16.1 Appendix 1](#).

⁵ Systemic AESI are identified as detailed in [Section 16.2 Appendix 2](#).

Statistical Analysis Plan

- TEAEs considered related to investigational product (IP), overall and by system organ class and preferred term
- Number of TEAEs considered related to IP by maximum severity, system organ class and preferred term
- TESAEs overall and by system organ class and preferred term
- TESAEs considered related to IP, overall and by system organ class and preferred term
- Adverse Events leading to treatment discontinuation overall and by system organ class and preferred term
- Application site disorders considered related to IP overall and by system organ class and preferred term
- Treatment emergent systemic AESI overall and by system organ class and preferred term
- Treatment emergent systemic AESI considered related to IP overall and by system organ class and preferred term
- Treatment emergent local AESI overall and by system organ class and preferred term

They were repeated overall and for each age group, in total and by initial actual treatment group on the SS for the whole treatment period, and on the OLS-500 for the Viaskin Milk 500 μ g open-label treatment period :

Additionally, tables showing the number and percentage of subjects who experienced at least one TEAE and the number of events by SOC and PT, summarizing TEAEs leading to:

- Epinephrine use:
 - o Standard medication name that contains "EPINEPHRINE" and ATC level 1 = "CARDIOVASCULAR SYSTEM"
- Systemic or inhaled corticosteroid use,
 - o ATC code starting with "H02", "R03AK", "R03BA"
- Topical corticosteroid use,
 - o ATC code starting with "D07"

were presented (exhaustiveness of the above selections, especially regarding the route that can be reported as "Other" with a text field specification, will be checked during the blind data review meeting) on the SS for the randomized blinded treatment period.

They were repeated on the SS for the whole treatment period, and on the OLS-500 for the Viaskin Milk 500 μ g open-label treatment period.

9.3.3.3 Subject-Year Analysis

A subject-year analysis was performed on the same parameter as described for the overview tables above on the whole treatment period overall and for each age-group for the SS. The subject year analysis should be presented according to treatments received (not randomized). E.g., subject randomized as placebo and treated during one year with Placebo then treated with Viaskin Milk 500 μ g during 2 years should account for 1 patient-year in Placebo column and 2 patient-year in Viaskin Milk 500 μ g column.

This document is confidential

Statistical Analysis Plan

Additionally, a subject-year analysis presented the total number of subject-years, the number of subjects with a TEAE (respectively a TEAE considered related to IP) per subject-year and the number of TEAEs (respectively TEAEs considered related to IP) per subject-year, for each dose level and by SOC and PT on the whole treatment period overall and for each age-group for the SS.

Separate listings were performed additionally:

- SAEs
- TESAEs
- Adverse events of specific interest (AESI):
 - o Local AESIs.

These local TEAEs of interest will be identified following methodology described in [16.1 Appendix 1](#).

- o Systemic AESI considered related to IP.
- o Systemic AESI (whether related or not).

These systemic TEAEs of interest will be identified following methodology described in [16.2 Appendix 2](#).

- AEs leading to discontinuation
- TEAEs leading to epinephrine intake

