8.1.7.1 Adverse Events

For adverse events analyses, serious adverse events elicited during DBPCFC will not be considered, they will be described separately.

All AEs and TEAEs will be listed and tabulated separately by Medical Dictionary for Regulatory Activities (MedDRA) System Organ Class (SOC) and Preferred Term. Incidence tables will be presented for all TEAEs and TESAEs for the reporting period as defined in [Section 7.3.2.1](#). The following tabulations will be produced overall and by age group, dose level and pooled placebo group on the Safety Set (SS) for the randomized blinded treatment period (Months 0 to 12):

- AEs and TEAEs overall and by system organ class and preferred term
- AEs and TEAEs by maximum severity, overall and by system organ class and preferred term
- TEAEs considered related to investigational product (IP), overall and by system organ class and preferred term
- Number of TEAEs and number of TEAEs considered related to IP by severity
- SAEs and TESAEs overall and by system organ class and preferred term
- SAEs and TESAEs by maximum severity, overall and by system organ class and preferred term
- TESAEs considered related to IP, overall and by system organ class and preferred term

- Viaskin Milk-induced local AEs overall and by system organ class and preferred term

In order to give an indication of longer term safety, a summary of AEs will be produced for a subset of subjects who received the highest safe dose determined during the study from Months 0 to 48. A subject-year analysis will present the total number of subject-years, the number of subjects with a TEAE (and respectively, a TEAE considered related to IP) per subject-year, and the number of TEAEs (and respectively, TEAEs considered related to IP) per subject-year, for each dose level.

Separate listings and tabulations will summarize:

- Systemic AESI whatever the causal relationship with IP.
- Local AESI.
- Severity of symptoms elicited during the DBPCFC.
- Discontinuations due to AEs will also be summarized.

Local and systemic AESI will be identified using systematic retrieval strategies that will be detailed in the SAP.

Adverse events occurring during the open-label treatment periods after Month 12 will be described. Details will be provided in the SAP.

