3.1 BRIEF DESCRIPTION

MILES study (V135-201) is a multi-centre, double-blind, placebo-controlled, randomized trial to study the safety and efficacy of Viaskin Milk applied epicutaneously every day to subjects from 2 to 17 years of age with IgE-mediated cow's milk allergy (CMA). Viaskin Milk is a patch containing an extract of cow's milk proteins. The placebo treatment consists of a Viaskin Milk patch containing a similar formulation without cow's milk proteins.

Subjects received blinded treatment for 1 year at one of the 3 doses of Viaskin Milk: 150 μ g, 300 μ g, or 500 μ g, or placebo. After the first year, all subjects received the highest dose of Viaskin Milk 500 μ g, and continued treatment in an open-label manner for up to a maximum of 3 additional years. Following results of the 12-month blinded period, all eligible subjects who wish to continue participation in the study were switched from Viaskin Milk 500 μ g to Viaskin Milk 300 μ g dose for 24 additional months of treatment.

The study is conducted at 17 sites in the United States and Canada, with selected investigators and staff experienced in the diagnosis and management of CMA and anaphylaxis, and who are capable of performing a DBPCFC in children (2 to 11 years old) and adolescents (12 to 17 years old).

Eligible subjects with confirmed IgE-mediated CMA performed a first DBPCFC at screening with escalating doses of cow's milk proteins. Subjects showing a positive DBPCFC at screening, defined as the appearance of objective signs or symptoms to an eliciting dose of cow's milk proteins \leq 300 mg (approximately 9.4 mL of cow's milk) were randomized in the study.

The study was divided into 2 consecutive parts for randomization of the subjects to treatment: Part A and Part B. Part A permitted an evaluation of the safety of 3 escalating doses of Viaskin Milk (150 μ g, 300 μ g, and 500 μ g cow's milk proteins) versus placebo in successive cohorts of subjects prior proceeding to Part B. Part B was designed to evaluate the efficacy and safety of the 3 selected safe doses (as determined from Part A) of Viaskin Milk versus placebo.

The efficacy of Viaskin Milk was assessed based on data pooled from subjects in both Part A and Part B. Details of subject enrolment and the treatments administered for each part of the study are provided in [Section 3.4](#).

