9.3.4.3 Subject-Year Analysis

Analysis by subject-year will be performed for the OLS-300 equivalently as described in [Section 9.3.3.3](#):

- a) The treatment durations and the respective AEs of subjects randomized to Placebo or Viaskin Milk 150 μ g in the DB-period will be assigned to the treatment arm "Placebo" or "Viaskin Milk 150 μ g", respectively.
- b) The treatment durations and the respective AEs of subjects randomized to Viaskin Milk 300 μ g in the DB-period and the whole OL-300 period will be added to the treatment arm "Viaskin Milk 300 μ g".

This document is confidential

Statistical Analysis Plan

- c) The treatment durations and the respective AEs of subjects randomized to Viaskin Milk 500µg in the DB-period and the whole OL-500 period will be added to the treatment arm "Viaskin Milk 500µg".

These treatment durations in days will be divided by 365.25 to get the subject-years. The number of AEs will be divided by the respective subject-years.

9.4 SYMPTOMS ELICITED DURING THE DBPCFC.

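### The rate of subjects with a TEAE per subject-year divides a once-per-subject count by all treatment time, so for common events it falls with longer exposure and favours the long open-label dose columns

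*SAP*

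**What the plan says.** SAP 9.3.3.3 attributes whole-treatment-period exposure and events to the treatment actually received. For each dose level it gives total subject-years and two rates. One is subject-based: "the number of subjects with a TEAE (respectively a TEAE considered related to IP) per subject-year". The other is event-based: "the number of TEAEs (respectively TEAEs considered related to IP) per subject-year, for each dose level and by SOC and PT". Protocol 8.1.7.1 has the same pair, the first worded as "the number of subjects with a TEAE (and respectively, a TEAE considered related to IP) per subject-year", and presents the analysis as an indication of longer-term safety.

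The SAP's worked example fixes the denominator. A subject given placebo for one year and then 500 µg for two years "should account for 1 patient-year in Placebo column and 2 patient-year in Viaskin Milk" 500 µg. The example attaches no condition about whether or when an event occurred.

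SAP 9.3.4.3 extends this to the 300 µg open-label analyses: "Analysis by subject-year will be performed for the OLS-300 equivalently". It adds the OL-500 period to the 500 µg column and the OL-300 period to the 300 µg column. It then states "These treatment durations in days will be divided by 365.25 to get the subject-years", followed by "The number of AEs will be divided by the respective subject-years". That last sentence gives only an event-count numerator. The subject-based rate enters through the reference back to 9.3.3.3.

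On exposure, SAP 3.1 states "Subjects received blinded treatment for 1 year at one of the 3 doses of Viaskin Milk", or placebo. Up to 3 open-label years at 500 µg were to follow, then 24 months at 300 µg after the amendment.

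**The concern.** A subject with a first event in month 2 counts once, and every later month on that treatment enlarges the denominator without being able to add to the numerator. Columns with different exposure per subject are then not on one scale.

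The design makes exposure unequal in a fixed direction. The placebo and 150 µg columns hold at most about one year per subject. In 9.3.3.3 the 500 µg column takes the open-label time of every arm, plus the blinded year of the 500 µg arm. In 9.3.4.3 the 300 µg column also becomes long.

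The whole-period and open-label incidence tables in SAP 9.3.3.2 and 9.3.4.2 are arranged by initial treatment group. The subject-year analysis is where long-term events are set against the treatment received. It covers the overview-table parameters, including any TEAE, related application-site disorders and local AESI. For those that are common, a reader comparing the subject-based rate across columns could take an effect of exposure length for an effect of dose.

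**Working it through.** **Step 1: reproduce the plan's figure.** With days on treatment divided by 365.25, one year on placebo gives 365.25/365.25 = 1 and two years on 500 µg give 730.5/365.25 = 2. Both match the example in SAP 9.3.3.3. A denominator stopped at the first event would give 1 and 2 only for a subject with no event on either treatment. The denominator is therefore all treatment time.

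**Step 2: inputs.**
- SAP 3.1 reports 198 randomized: 18 in Part A and 180 in Part B.
- Part A (SAP 3.4.1): 3 cohorts of 6 at 2:1, giving 4 per dose and 6 placebo.
- Part B (SAP 3.4.2.1): 1:1:1:1, taken as 180/4 = 45 per arm. This is an assumption.
- Totals: 51 placebo and 49 per dose.
- Also assumed: no dropout, and the same constant first-event hazard L per year in every column. The documents give no TEAE rates, so L is a range.

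**Step 3: formulas.** A subject followed for T years has an event with probability 1 − exp(−L·T).
- Placebo, 1 year: 1 − exp(−L).
- 500 µg column with t open-label years: [149·(1 − exp(−L·t)) + 49·(1 − exp(−L·(1+t)))] / [149·t + 49·(1+t)], where 149 = 51 + 49 + 49.
- Subject-years: t = 2 gives 298 + 147 = 445; t = 3 gives 447 + 196 = 643.

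Example, L = 1 and t = 2: numerator 149 × 0.8647 + 49 × 0.9502 = 175.4, and 175.4/445 = 0.394. Placebo is 0.632, so the ratio is 0.62.

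**Step 4: results at truly equal risk.**

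| L per year | Placebo rate | 500 µg rate, t = 2 | Ratio, t = 2 | Ratio, t = 3 |
|---|---|---|---|---|
| 0.05 | 0.0488 | 0.0472 | 0.968 | 0.945 |
| 0.1 | 0.0952 | 0.0892 | 0.938 | 0.895 |
| 0.5 | 0.3935 | 0.2972 | 0.755 | 0.625 |
| 1 | 0.6321 | 0.3941 | 0.624 | 0.467 |
| 2 | 0.8647 | 0.4385 | 0.507 | 0.355 |

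The 300 µg column in 9.3.4.3 has the same structure, with 2 OL-300 years for all subjects plus the blinded year for the 300 µg arm. Assuming everyone switched, its ratios to placebo at L = 0.1, 0.5, 1 and 2 are again 0.94, 0.76, 0.62 and 0.51.

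**Step 5: a true difference.** If 500 µg doubled the hazard, with t = 2, the planned ratio would be 1.68 at placebo L = 0.1, 1.00 at L = 0.5 and 0.69 at L = 1.

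**Step 6: time-at-risk denominator.** Expected time to first event or end of treatment is (1 − exp(−L·T))/L per subject, so events over time at risk equals L in every column and the ratio is 1.00. A simulation at L = 1, t = 2 gave 1.01 per year, against 0.39 with the planned denominator.

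**Step 7: limit of that remedy.** Take an assumed hazard of 4 per year for the first 3 months and 0.2 afterwards. The event-free proportion is exp(−1) = 0.368 at 3 months, 0.317 at 1 year and 0.259 at 2 years.
- At 1 year, time at risk is (1 − 0.368)/4 + (0.368 − 0.317)/0.2 = 0.414, and 0.683/0.414 = 1.65.
- At 2 years, time at risk is 0.701, and 0.741/0.701 = 1.06.
- The planned rates would be 0.683/1 = 0.683 and 0.741/2 = 0.370.

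The 2-year to 1-year ratio is 0.64 with time at risk and 0.54 as planned. The artefact shrinks but the columns still differ.

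**The case against.** The strongest reply is that the plan already reports what is needed. The event-count rate stands beside the subject-based rate, by treatment received, with total subject-years shown. The overview and incidence tables in SAP 9.3.3.1 and 9.3.3.2 compare the arms over the 12-month blinded period, where planned exposure is equal. No test or decision rule is attached to the subject-year analysis. All of this stands, and it confines the problem to one descriptive rate.

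The scope is also narrower than it may look. A reader might infer that the 300 µg column is favoured throughout. In 9.3.3.3 it is not: the compliance text for the double-blind and OL-500 analyses (SAP 9.2) ends the whole treatment period at the switch, so only 500 µg is long there. In 9.3.4.3 the only numerator written out is a count of AEs, and the subject-based rate depends on the cross-reference.

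The size depends on assumed hazards. At 0.1 per year with 2 open-label years the ratio moves by about 6%, so most rare preferred terms would be unaffected in practice.

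Finally, early-concentrated risk is plausible, since protocol 6.3.1 and 6.3.2 step up daily wear time for safety at the start of treatment. Step 7 shows that time at risk is then not constant either. This limits the remedy. It does not justify the planned denominator.

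**Conclusion.** The concern holds for the subject-based rate. For common events it falls with exposure at equal risk, favouring 500 µg over placebo in 9.3.3.3, and 500 µg and 300 µg over placebo and 150 µg in 9.3.4.3. The bias is large where most subjects have an event and negligible for rare terms. The figures rest on equal constant hazards, no dropout, 45 per arm in Part B and full switching to 300 µg.

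A reader might go further and infer that the trial's safety reporting will make the active doses look safer than placebo, or will hide harm. The documents do not support that. The unaffected event-count rate and the 12-month comparison are both planned, and the doubling in Step 5 is hypothetical because no TEAE rates are given. This is a correctable defect in one long-term descriptive summary.

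**What to change.** 1. For the subject-based rate in the OL-300 and final analyses, use as denominator the time from the first patch on that treatment to the first such event, or to the end of that treatment if there is none.
2. Keep total subject-years for the event-count rate only.
3. State in SAP 9.3.4.3 which numerators are used, so that the subject-based rate does not depend on the cross-reference.
4. Footnote the subject-based rate already produced for the OL-500 analysis as not comparable across columns with different exposure.
5. Footnote the revised rate too: it is not fully comparable across columns if the hazard changes over time.

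The cost is SAP wording and minor programming with AE onset and treatment dates already collected. SAP section 2 says the double-blind and OL-500 analyses have been run and are kept for traceability, so the prospective change belongs in the OL-300 and final analyses. The footnote in item 4 avoids re-running completed work.

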9.3.4 OL-300 Analyses

9.3.4.1 Overview tables

An overview of TEAEs occurring in the analyzed OL-300 period will be presented for the OLS-300 overall and for each age group, in total and by initial actual treatment group (placebo/dose level/overall active) as specified in [Section 9.3.3.1](#).

9.3.4.2 Incidence tables

The incidence tables - described in [Section 9.3.3.2](#) - will be repeated overall and for each age group, in total and by initial actual treatment group (placebo/dose level/overall active) on the OLS-300 for the analyzed OL-300 period.

The listings described in [Section 9.3.3.2](#) will include the adverse events starting in OL-300 period.

9.3.4.3 Subject-Year Analysis

Analysis by subject-year will be performed for the OLS-300 equivalently as described in [Section 9.3.3.3](#):

- a) The treatment durations and the respective AEs of subjects randomized to Placebo or Viaskin Milk 150 μ g in the DB-period will be assigned to the treatment arm "Placebo" or "Viaskin Milk 150 μ g", respectively.
- b) The treatment durations and the respective AEs of subjects randomized to Viaskin Milk 300 μ g in the DB-period and the whole OL-300 period will be added to the treatment arm "Viaskin Milk 300 μ g".

This document is confidential

Statistical Analysis Plan

- c) The treatment durations and the respective AEs of subjects randomized to Viaskin Milk 500µg in the DB-period and the whole OL-500 period will be added to the treatment arm "Viaskin Milk 500µg".

These treatment durations in days will be divided by 365.25 to get the subject-years. The number of AEs will be divided by the respective subject-years.

9.4 SYMPTOMS ELICITED DURING THE DBPCFC.

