Following results of the 12-month blinded period, all eligible subjects will switch from Viaskin Milk 500 µg to Viaskin Milk 300 µg for 24 additional months, independently of the duration of previous treatment with Viaskin Milk 500 µg:

- Subjects who will decline to switch to Viaskin Milk 300 µg will be discontinued from the study and an ET visit or an EOS visit will be performed (see [Section 7.2.3](#));
- Subjects who will switch to Viaskin Milk 300 µg will be treated for 24 additional months:
 - Until Visit S1 is performed and the subjects start with Viaskin Milk 300 µg, they will continue to receive Viaskin Milk 500 µg. No DBPCFC should be performed while the subjects are still receiving Viaskin Milk 500 µg.
 - Subjects will then follow a dedicated study flowchart (see [Table 6](#) and [Table 7](#)),
 - Optional DBPCFCs can be performed after 12 and/or 24 months of treatment,

If the decision is made by the Investigator and the subject to perform a DBPCFC, its performance must comply with the standardized methodology defined in [Section 7.3.1.1](#). Standardized milk and placebo food challenge formula and material as well as the Manual of Procedures will be provided to all sites and must be used for conducting the food challenge.

When performed, the results of these food challenge(s) will be documented and reported in the e-CRF.

- The EOS visit will take place 2 weeks after the end of the treatment period.

[figure not shown]
During their participation in the study all subjects will be instructed to remain on a strict cow's milk-free diet with no consumption of dairy products or baked milk products until their final study visit (except during DBPCFC). At the end of participation in the study, the re-introduction of milk products (eg, dairy products or baked milk products) into the subject's diet, or the decision to keep the subject under a strict cow's milk-free diet will be left to the Investigator's discretion.

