8.1.1 Datasets or Populations Analyzed

The Safety Set (SS) will include all subjects who applied at least 1 Viaskin patch. Subjects will be analyzed according to treatment received. In case of wrong dispensation, the subject will be analyzed according to the treatment received the longest, or as it will be determined at the Blind Data Review Meeting (BDRM), on a case-by-case basis. The SS will be used for all safety analysis tables and listings.

The Intent-to-Treat Set (ITT) will include all randomized subjects. Subjects will be analyzed according to randomized treatment. The ITT Set will be used for all analyses of efficacy endpoints.

The Per Protocol Set (PPS) will include all subjects from the ITT population who do not have major protocol violations that may affect the primary endpoint. Major protocol deviations will be defined in the SAP.

Protocol deviations will be categorized as either major or minor and discussed during the blinded data review meeting (BDRM). Decisions taken at the BDRM will be documented and approved by DBV prior to database lock and unblinding the study.

The Open-label Sets (OLS) will include all subjects from the ITT who entered the open-label treatment period (ie, who applied at least one Viaskin Milk patch during the open-label treatment period) and will be described in the SAP.

The Open-label Set 300 µg (OLS_300) will include all subjects who switched to Viaskin Milk 300 µg and will be described in the SAP.

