5.3 SAFETY SET (SS)

The Safety Set includes all subjects who applied at least 1 Viaskin patch. Subjects will be analyzed according to treatment received. In case of wrong dispensation, the subject

This document is confidential

Statistical Analysis Plan

will be analyzed according to the treatment received the longest, or as will be determined at the BDRM, on a case-by-case basis.

The safety set will be used for all safety analysis tables and listings, which include the randomized blinded treatment period.

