5.6 OPEN-LABEL SET 300 (OLS-300)

The Open-Label Set 300 will include all subjects who entered the open-label treatment period after switch to Viaskin Milk 300 μ g and applied at least one Viaskin Milk 300 μ g patch during this open-label period.

Analyses of the Viaskin Milk 300 μ g open-label treatment period will be run on the OLS-300.

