9 SAFETY

The Safety Set was employed for all safety analyses on the randomized blinded treatment period and on the whole treatment or study period; OLS-500 was used for all safety analyses on the OL-500 period and OLS-300 will be used for the OL-300 period.

Safety analysis will generally be performed on the actual treatments given. In case of wrong dispensation, the subject will be analyzed according to the treatment received the longest.

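### The subject-year safety table for the 300 µg open-label period includes only subjects who switched, yet counts pre-switch time, against the plan's own Safety Set rule

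*SAP*

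**What the plan says.** SAP 9.3.4.3 opens: "Analysis by subject-year will be performed for the OLS-300 equivalently as described in" SAP 9.3.3.3. It then fills four columns:

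- Placebo and 150 µg: double-blind time and AEs only.
- 300 µg: double-blind time of the 300 µg arm plus the whole OL-300 period.
- 500 µg: time of the 500 µg arm "in the DB-period and the whole OL-500 period will be added to the treatment arm" for 500 µg.

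The set is defined in SAP 5.6: "The Open-Label Set 300 will include all subjects who entered the open-label treatment period after switch to Viaskin Milk" 300 µg, with at least one 300 µg patch applied.

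The rules on which set to use are:

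- SAP 5.3: "The safety set will be used for all safety analysis tables and listings, which include the randomized blinded treatment period".
- SAP 9: "The Safety Set was employed for all safety analyses on the randomized blinded treatment period and on the whole treatment or study period"; OLS-500 and OLS-300 serve the OL-500 and OL-300 periods respectively.
- SAP 9.3.3.3, the section being followed: Safety Set, whole treatment period, by treatment received.
- Protocol 8.1.1: "The SS will be used for all safety analysis tables and listings".

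SAP 12.5 and 12.6 declare no departure from protocol amendments 5 and 6.

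**The concern.** The table mixes a set defined by what happened at the switch with time that came before it. Several groups never enter OLS-300: subjects who withdrew during the blinded year or on 500 µg, subjects who failed the switch criteria in Protocol 4.4.2 (a new disorder, or compliance below 80%), and subjects who declined. Under Protocol 3.1.4, those who decline "will be discontinued from the study and an ET visit or an EOS visit will be performed". All of them lose both their AEs and their exposure from every column.

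This matters most in the rows on stopping treatment. SAP 9.3.3.3 applies the subject-year method to the parameters of the overview tables, and SAP 9.3.3.1 lists among these TEAEs leading to treatment discontinuation and AEs leading to death. A reader who finds none of these in the placebo column could take it as a finding about placebo, when the choice of set made it impossible to see any.

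**Working it through.** The plan states no rate or number on this point, so there is no figure to reproduce. The conflict is shown from the text; the arithmetic only indicates scale.

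**1. Which set the rules give.** The columns include double-blind time, so SAP 5.3 applies directly. Together they span double-blind, OL-500 and OL-300, so the whole-treatment-period rule in SAP 9 applies as well. OL-500 time taken alone would go on OLS-500, but this is a combined table. Under either the Safety Set or OLS-500, subjects who left during OL-500 would be counted; under OLS-300 they are not.

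**2. What cannot appear.** Discontinuation or death before the switch excludes a subject from OLS-300. The placebo and 150 µg columns end at Month 12, so no such event can enter them. The same holds for the 500 µg column, because Table 1 ends OL-500 at the switch visit. The 300 µg column continues into OL-300 and can show discontinuations and deaths there. An AE that began before the switch but led to stopping after it could still be counted. This step needs no assumption about rates.

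**3. Column sizes.** Part A has three cohorts of 4 active and 2 placebo (Protocol 3.1.2). Part B randomized 180 at 1:1:1:1 (SAP 3.4.2.1), here taken as an even split.

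- Each dose: 180/4 + 4 = 49. Placebo: 180/4 + 6 = 51. Total 3 × 49 + 51 = 198, as stated in SAP 3.1.
- With near-complete follow-up, one double-blind discontinuation missing from the table is worth 100/51 = 1.96 (placebo) or 100/49 = 2.04 (150 µg) per 100 subject-years.
- Double-blind share of the 300 µg column, if all 198 switch: 49/(49 + 2 × 198) = 49/445 = 11% with two full OL-300 years, or 49/(49 + 198) = 20% at the Year 1 analysis.

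**4. Effect on a double-blind rate (assumed inputs).** Let d be the share of an arm that does not switch, e the double-blind years those subjects contribute, and k their AE rate relative to switchers. Then

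OLS-300 rate / Safety Set rate = [(1 − d) + de] / [(1 − d) + dek].

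| k | d = 0.1, e = 0.5 | d = 0.3, e = 1 |
|---|---|---|
| 0.5 | 0.95/0.925 = 1.03 | 1/0.85 = 1.18 |
| 1 | 1.00 | 1.00 |
| 2 | 0.95/1.00 = 0.95 | 1/1.30 = 0.77 |
| 3 | 0.95/1.05 = 0.90 | 1/1.60 = 0.63 |

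The share of subject-years lost is de/[(1 − d) + de]: 0.05/0.95 = 5% and 0.3/1 = 30% in the two columns.

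**5. Does OLS-300 distort the 300 µg/placebo ratio?** Suppose no dose effect and a rate of 1 in every switcher. OLS-300 then gives 1.00. On the Safety Set, with two OL-300 years per switcher (2 × 198 = 396 before the factor 1 − d):

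- d = 0.1, k = 2, e = 0.5: placebo 1/0.95 = 1.053; 300 µg (49 × 1.00 + 396 × 0.9)/(49 × 0.95 + 396 × 0.9) = 405.4/402.95 = 1.006; ratio 0.956.
- d = 0.3, k = 3, e = 1: placebo 1.600; 300 µg (49 × 1.6 + 396 × 0.7)/(49 + 396 × 0.7) = 355.6/326.2 = 1.090; ratio 0.681.

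In this model the Safety Set ratio departs from 1, because only switchers can supply OL-300 time. The Safety Set corrects each pre-switch rate but does not make the columns comparable.

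**The case against.** **The events are reported elsewhere.** This stands. SAP 9.3.3.1 to 9.3.3.3 report pre-switch events on the Safety Set, including a subject-year analysis. SAP 2.2.1 promises the complete analysis at study end, and Table 1 runs the whole treatment period from first to last treatment, so 9.3.3.3 might be rerun with OL-300 time included. However, the compliance text in SAP 9.2 describes the whole treatment period as ending at the switch, and the SAP does not say which reading governs. The loss is confined to the 9.3.4.3 table.

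**A switchers-only cohort may be intended.** It compares largely the same people before and after, which has merit, as step 5 shows. But 9.3.4.3 neither says so nor labels the table that way, and it claims equivalence with a Safety Set analysis.

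**OLS-300 carries pre-switch data in other sections.** True for whole-period exposure and compliance (SAP 9.1.3 and 9.2.2) and for Month 0 and Month 12 reference values (for example SAP 9.5.3). Those are not AE rates. The neighbouring AE sections, 9.3.4.1 and 9.3.4.2, restrict OLS-300 to the OL-300 period, and 9.4.2 returns to the Safety Set for SAEs during any food challenge.

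**The direction is not known.** This stands. Low compliance may mean less patch exposure and fewer reactions, and declining need have nothing to do with AEs.

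**The protocol leaves the set open.** Protocol 8.1.7.1 names no set in its subject-year sentence, which sits in a paragraph on longer-term safety. The general rule in Protocol 8.1.1 still covers it.

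**Conclusion.** The inconsistency is established from the text. So is its direct consequence: pre-switch leavers are absent from every column, and the placebo and 150 µg columns cannot show a TEAE that led to discontinuation or death before the switch. Pre-switch AE rates in the table describe switchers only. Whether they are too low, too high or unbiased depends on how leavers' rates compare with switchers'. The documents give neither dropout numbers nor AE rates, so the figures in step 4 are illustrations, not estimates.

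A reader might infer that the 300 µg/placebo AE-rate ratio in this table is too high. The documents do not support that. The Safety Set ratio is not a clean reference, since it sets all-subject double-blind time against OL-300 time from switchers only.

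The table is descriptive and no test depends on it. It should still be corrected, because it conflicts with the plan's own rule and is the one subject-year table that explicitly includes OL-300 exposure.

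**What to change.** In SAP 9.3.4.3:

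1. Run the combined-period subject-year table on the Safety Set by treatment actually received, extending the attribution rule of 9.3.3.3 to OL-300 time. In items a) to c), assign time by treatment received instead of by randomized arm. This is a wording conflict only, as no misdispensing is documented.
2. State that the table covers the whole treatment period as defined in Table 1, which settles the different reading in SAP 9.2.
3. Limit any OLS-300 version to OL-300-period exposure and events, as 9.3.4.1 and 9.3.4.2 already do.
4. Footnote that 300 µg and 500 µg open-label time comes only from subjects who continued, so the columns are not a like-for-like dose comparison.

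Keep the rate formula unchanged. The cost is SAP wording and re-programming of one descriptive table family; no new data are needed.
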